7.3 Subject Population(s) for Analysis

All subjects will be used for analysis.

8 Safety and Adverse Events

8.1 Definitions

Unanticipated Problems Involving Risk to Subjects or Others

Any incident, experience, or outcome that meets all of the following criteria:

- Unexpected in nature, severity, or frequency (i.e. not described in study-related documents such as the IRB-approved protocol or consent form, the investigators brochure, etc)
- Related or possibly related to participation in the research (i.e. possibly related means there is a reasonable possibility that the incident experience, or outcome may have been caused by the procedures involved in the research,
- Serious (as defined below) “Serious” is different than “severe” as reported in the CTC criteria that applies a grade to the AE.

Adverse Event

An **adverse event** (AE) is any symptom, sign, illness or experience that develops or worsens in severity during the course of the study. Intercurrent illnesses or injuries should be regarded as adverse events. Abnormal results of diagnostic procedures are considered to be adverse events if the abnormality:

- results in study withdrawal
- is associated with a serious adverse event
- is associated with clinical signs or symptoms
- leads to additional treatment or to further diagnostic tests
- is considered by the investigator to be of clinical significance

Serious Adverse Event

Adverse events are classified as serious or non-serious. A **serious adverse event** is any AE that is:

- fatal
- life-threatening
- requires or prolongs hospital stay
- results in persistent or significant disability or incapacity
- a congenital anomaly or birth defect
- an important medical event

Important medical events are those that may not be immediately life threatening but are clearly of major clinical significance. They may jeopardize the subject and may require intervention to prevent one of the other serious outcomes noted above. For example, drug overdose or abuse, a seizure that did not result in in-patient hospitalization, or intensive treatment of bronchospasm in an emergency department would typically be considered serious.

All adverse events that do not meet any of the criteria for serious should be regarded as **non-serious adverse events**.

Adverse Event Reporting Period

The study period during which adverse events must be reported is normally defined as the period from the initiation of any study procedures to the end of the study treatment follow-up. For this study, the study treatment follow-up is defined as 30 days following the last administration of study treatment.

Preexisting Condition

A preexisting condition is one that is present at the start of the study. A preexisting condition should be recorded as an adverse event if the frequency, intensity, or the character of the condition worsens during the study period.

General Physical Examination Findings

At screening, any clinically significant abnormality should be recorded as a preexisting condition. At the end of the study, any new clinically significant findings/abnormalities that meet the definition of an adverse event must also be recorded and documented as an adverse event.

Post-study Adverse Event

All unresolved adverse events should be followed by the investigator until the events are resolved, the subject is lost to follow-up, or the adverse event is otherwise explained. At the last scheduled visit, the investigator should instruct each subject to report any subsequent event(s) that the subject, or the subject's personal physician, believes might reasonably be related to participation in this study. The investigator should notify the study sponsor of any death or adverse event occurring at any time after a subject has discontinued or terminated study participation that may reasonably be related to this study. The sponsor should also be notified if the investigator should become aware of the development of cancer or of a congenital anomaly in a subsequently conceived offspring of a subject that has participated in this study.

Abnormal Laboratory Values

A clinical laboratory abnormality should be documented as an adverse event if any one of the following conditions is met:

- The laboratory abnormality is not otherwise refuted by a repeat test to confirm the abnormality
- The abnormality suggests a disease and/or organ toxicity
- The abnormality is of a degree that requires active management; e.g. change of dose, discontinuation of the drug, more frequent follow-up assessments, further diagnostic investigation, etc.

Hospitalization, Prolonged Hospitalization or Surgery

Any adverse event that results in hospitalization or prolonged hospitalization should be documented and reported as a serious adverse event unless specifically instructed otherwise in this protocol. Any condition responsible for surgery should be documented as an adverse event if the condition meets the criteria for an adverse event.

Neither the condition, hospitalization, prolonged hospitalization, nor surgery are reported as an adverse event in the following circumstances:

- Hospitalization or prolonged hospitalization for diagnostic or elective surgical procedures for a preexisting condition. Surgery should **not** be reported as an outcome of an adverse event if the purpose of the surgery was elective or diagnostic and the outcome was uneventful.
- Hospitalization or prolonged hospitalization required to allow efficacy measurement for the study.
- Hospitalization or prolonged hospitalization for therapy of the target disease of the study, unless it is a worsening or increase in frequency of hospital admissions as judged by the clinical investigator.

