3.1 General Design

This study is a pilot cross-sectional study.

Study Schema:

Any patient with a familial syndrome at risk of kidney cancer (VHL, BHD, HLRCC or TSC) undergoing annual imaging screening is eligible, but we will target inclusion of at least 10 subjects who have at least 1 kidney lesion. Therefore, up to 5 subjects may have no current kidney lesions. Subject participation will be

only for the day of CEUS study. There will be no follow-up period for this study. However, if results are encouraging, a longitudinal observational study may follow, and these same subjects would be eligible for enrollment.

Abdominal imaging in patients with VHL is also used to monitor the pancreas. Although pancreatic lesions are less common than kidney lesions, cross-sectional imaging allows for monitoring of both organs. For patients with VHL, we will image the pancreas in addition the kidneys in order to establish parameters for pancreas CEUS. CEUS of the pancreas is not novel⁵¹, but its use for screening in patients at risk of pancreas lesions has not been investigated.

Following completion of imaging, all CEUS, MRI (within 4 months) and B-mode (at time of CEUS) US studies will be de-identified. Blinded radiologists will interpret images and provide an overall assessment of risk of malignancy to each kidney using the Bosniak criteria for each kidney lesion present. The Bosniak criteria places cystic lesions into one of 5 categories (I, II, IIF, III and IV) based on lesion characteristics. CEUS based diagnosis will be compared to the diagnoses on routine B-mode US and contrast-enhanced MRI.

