3.4 Primary Safety Endpoints

- Adverse effects of microbubble contrast administration.
- Development of hematuria post-CEUS.

4 Subject Selection and Withdrawal

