4.4.2 Data Collection and Follow-up for Withdrawn Subjects

Any subject who is withdrawn from the study will be followed in the immediate post-imaging period and for 72 hours following contrast administration, if contrast agent was administered, for the purpose of detecting any unanticipated adverse effect of contrast administration. If no contrast agent was administered, follow-up will not be required. Since this is a cross-sectional study, and subjects are not being followed longitudinally, subjects that withdraw will also not be followed beyond the 72-hour post-imaging period if complete resolution of any adverse events is noted at 72 hours. If adverse effects are persistent, subjects will continue to be followed until resolution of adverse effects.

5 Study Drug

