5.9.4 Return or Destruction of Study Drug

At the completion of the study, there will be a final reconciliation of drug shipped, drug consumed, and drug remaining. This reconciliation will be logged on the drug reconciliation form, signed and dated. Any discrepancies noted will be investigated, resolved, and documented prior to return or destruction of unused study drug. Drug destroyed on site will be documented in the study files.

6 Study Procedures

6.1 Visit 1

After consent is signed, urinalysis and pregnancy test (if necessary) will be obtained. If the subject is cleared to proceed, IV access will be placed. Baseline B-mode US will be performed to confirm the lesions being imaged (unless it is a subject with no lesions, then a basic B-mode US will be performed). Contrast agent will be prepared by trained nursing staff. Once all study members and subject are prepared, contrast agent will be administered, and contrast enhancement of each lesion captured on a video clip. Once all lesions of interest are imaged, IV will be discontinued, and the subject discharged. Subject will be monitored throughout the study for any adverse events. See Flowchart (Appendix 1) for details.

Due to the uncommon occurrence of serious cardiopulmonary reactions, as listed in the package insert, resuscitation equipment and trained personnel will always be readily available during the study visit.

Subjects may be asked to return for an additional imaging visit the following 1-2 years for a repeat study to mirror clinical protocols for imaging in VHL.

7 Statistical Plan

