8.2 Recording of Adverse Events

At each contact with the subject, the investigator must seek information on adverse events by specific questioning and, as appropriate, by examination. Information on all adverse events should be recorded immediately in the source document, and also in the appropriate adverse event module of the case report form (CRF). All clearly related signs, symptoms, and abnormal diagnostic procedures results should be recorded in the source document, though should be grouped under one diagnosis.

All adverse events occurring during the study period must be recorded. The clinical course of each event should be followed until resolution, stabilization, or until it has been determined that the study treatment or participation is not the cause. Serious adverse events that are still ongoing at the end of the study period must be followed up to determine the final outcome. Any serious adverse event that occurs after the study period and is considered to be possibly related to the study treatment or study participation should be recorded and reported immediately.

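### All adverse events must be recorded for 30 days after contrast, but subjects who complete the visit have no scheduled adverse-event contact after discharge, while withdrawn dosed subjects are followed for 72 hours

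*Combined protocol and SAP*

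**What the plan says.** Five parts of the protocol bear on how long subjects are watched for AEs after contrast.

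- **Reporting period (section 8.1).** "For this study, the study treatment follow-up is defined as 30 days following the last administration of study treatment".
- **Recording rule (section 8.2).** "All adverse events occurring during the study period must be recorded". The rule is not limited to serious or related events. The same section has the investigator ask about AEs whenever there is contact with the subject.
- **Design and visit (sections 3.1 and 6.1).** Participation is the imaging day only: "There will be no follow-up period for this study". At the end of the visit, "Once all lesions of interest are imaged, IV will be discontinued, and the subject discharged". Section 6.1 also allows an optional repeat imaging visit 1-2 years later.
- **Withdrawn subjects (section 4.4.2).** "Any subject who is withdrawn from the study will be followed in the immediate post-imaging period and for 72 hours following contrast administration", provided contrast was given. If events have resolved by then, "subjects that withdraw will also not be followed beyond the 72-hour post-imaging period".
- **Schedule (Appendix 1).** AE assessment is marked under the CEUS study and Early Termination columns. Footnote 6 places it during the CEUS study. The Post-CEUS column holds only the collection of other imaging.

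For later events, section 8.1 has subjects told at the last visit to report anything that they or their own doctor "believes might reasonably be related to participation in this study". Section 3.4 lists "Adverse effects of microbubble contrast administration" as a primary safety endpoint, together with hematuria after CEUS.

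**The concern.** The protocol gives three different answers to how long a dosed subject is under AE surveillance: 30 days, 72 hours, or the visit day only. The longest carries the recording obligation, and the shortest is what the schedule provides for completers.

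As section 8.2 is written, AEs are found by asking at contacts. With no contact after discharge, a completer's new event reaches the file only if the subject volunteers it and someone already believes it is related. The final safety table could then report no post-discharge events without showing whether there were none or nobody asked. The recording rule could not be shown to have been met.

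Follow-up is also uneven. Someone withdrawn after contrast is followed for 72 hours. Someone who completes imaging, with up to 7 injections allowed by section 5.2, is not.

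**Working it through.** The protocol gives no figure to reproduce here. The check sets the provisions side by side and then sizes the gap.

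**1. Provisions compared**

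| Source | Who | Time after contrast | Scheduled AE contact after discharge |
|---|---|---|---|
| 8.1 and 8.2 | All subjects | 30 days, all AEs | None specified |
| 3.1 and 6.1 | Completers | Visit day | None |
| Appendix 1, footnote 6 | Completers | During the CEUS study | None; the Post-CEUS column has imaging collection only |
| 4.4.2 | Withdrawn after contrast | 72 hours, longer if an AE persists | Follow-up stated, means not specified |
| 8.1, post-study events | All subjects | Open-ended | None; self-report of events believed related |

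The Appendix 1 table was extracted from PDF, but footnote 6 and section 3.1 independently agree with this reading of its columns.

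**2. Coverage of the 30-day window**

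- Window: 30 × 24 = 720 hours.
- Withdrawn dosed subject: 72 / 720 = 10%, or 3 of 30 days.
- Completer: 0 scheduled contacts after discharge. If nobody withdraws, this applies to 15 of 15 subjects.
- Hours 72 to 720, which is 27 days: nothing is scheduled for anyone without a persisting event.
- The optional repeat visit at 1-2 years falls outside every window.

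**3. Could other provisions fill the gap?**

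- *Self-report (8.1).* It is passive and filtered by belief about causality, so it is narrower than the all-AE rule in 8.2.
- *Following unresolved AEs to resolution (8.1, 8.2).* This applies only once an event has been detected.
- *Post-CEUS urinalysis (Appendix 1, footnote 5).* It is marked in the CEUS study column, so it covers the visit. Hematuria noticed after discharge is not asked about.

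**4. How many serious events might fall in the gap?**

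Section 1.2 reports, for perflutren lipid, 11 serious events arising 2-15 days after administration among 1716 subjects. Assuming that rate applied here, with one event per subject:

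- Rate: 11 / 1716 = 0.00641, or 0.64%.
- Expected in 15 subjects: 15 × 0.00641 = 0.096.
- Probability of at least one: 1 − (1 − 0.00641)^15 = 9.2%.

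These are serious events of any cause. Section 1.2 attributes all 11 to progression of underlying disease, so the figures do not estimate missed contrast effects. The documents give no rate for non-serious events arising after discharge, so that part of the gap cannot be sized.

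**The case against.** The strongest case on the other side is about weight.

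- **Reactions are acute.** In section 1.2 the reactions that led to discontinuation began within 1-15 minutes, and most serious cardiopulmonary reactions occur within 30 minutes. The plan monitors throughout the visit, records vital signs, takes urine before and after, and observes for at least 30 minutes after any possible reaction. This stands: the period of highest risk is covered.
- **The endpoint is narrower than all AEs.** Section 3.4 names contrast effects and hematuria, and the self-report instruction largely matches the first. This stands in part. The mismatch with the all-AE rule lies mainly in unrelated events. Even for related events, though, a passive report cannot separate silence from absence.
- **The serious-event rate does not transfer.** It comes from trials of an agent studied mostly in cardiac patients, while this trial excludes active cardiac disease. This stands, and it pushes the expected count below 0.10.
- **Withdrawn subjects may need closer follow-up.** The reasons for withdrawal include AEs and illness, so some difference is defensible. But section 4.4.2 gives its purpose as detecting unanticipated contrast effects, which applies equally to completers. Its word *also* hints that one window was meant for everyone, yet no text gives it to completers.
- **Section 3.1 may mean only that there is no longitudinal study follow-up, and a reporting window need not imply a contact.** The first reading is possible. It does not help, because section 8.2 requires all AEs to be recorded and no scheduled contact supports that.
- **The consent form was not available.** It may contain discharge instructions. These could strengthen self-reporting but would not create a scheduled contact in the protocol.

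**Conclusion.** The concern holds. As written, the plan cannot show that it meets its own 30-day, all-AE recording rule for subjects who complete the visit, and it follows withdrawn dosed subjects more actively than completers. The size is 0 scheduled post-discharge contacts for up to 15 of 15 subjects, against 72 hours (10% of the window) for those withdrawn after contrast.

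The practical risk is modest. The expected number of serious events in the gap is at most about 0.10 if the pre-market rate applies, and probably lower in this population. What is lost is complete and consistent ascertainment of a primary safety endpoint. The agreement analyses are not touched. The change should be made because the contradiction is plain and cheap to remove.

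The conclusion assumes that the Appendix 1 columns were extracted correctly and that the removed consent pages do not schedule a later contact.

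**What to change.** Choose one AE ascertainment window for every subject who receives contrast, whether completing or withdrawn, and align sections 3.1, 4.4.2 and 8.1 and Appendix 1 to it. In the Post-CEUS column of Appendix 1, add one phone contact at the end of the window with direct AE questions, including visible blood in the urine. Record *not reached* when a call fails, so that a missing answer is not counted as no event.

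Either window removes the contradiction:

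- **30 days** keeps section 8.1 as it is and covers the 2-15-day span of the late events in section 1.2.
- **72 hours** matches section 4.4.2 and the acute profile of the agents, but would miss most of that later span. Section 8.1 would then have to be shortened.

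The cost is wording in four places and about 15 short calls. No procedure or visit is added.

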8.2 Recording of Adverse Events

At each contact with the subject, the investigator must seek information on adverse events by specific questioning and, as appropriate, by examination. Information on all adverse events should be recorded immediately in the source document, and also in the appropriate adverse event module of the case report form (CRF). All clearly related signs, symptoms, and abnormal diagnostic procedures results should be recorded in the source document, though should be grouped under one diagnosis.

All adverse events occurring during the study period must be recorded. The clinical course of each event should be followed until resolution, stabilization, or until it has been determined that the study treatment or participation is not the cause. Serious adverse events that are still ongoing at the end of the study period must be followed up to determine the final outcome. Any serious adverse event that occurs after the study period and is considered to be possibly related to the study treatment or study participation should be recorded and reported immediately.

8.3 Reporting of Serious Adverse Events and Unanticipated Problems

Investigators must conform to the adverse event reporting timelines, formats and requirements of the various entities to which they are responsible, but at a minimum those events that must be reported are those that are:

- related to study participation,
- unexpected, and
- serious or involve risks to subjects or others
(see definitions, section 8.1).

If the report is supplied as a narrative, the minimum necessary information to be provided at the time of the initial report includes:

- | | |
|---|--|
| 
• Study identifier• Study Center• Subject number• A description of the event• Date of onset | 
• Current status• Whether study treatment was discontinued• The reason why the event is classified as serious• Investigator assessment of the association between the event and study treatment |
|---|--|

8.3.1 Investigator reporting: notifying the study sponsor

Not applicable as there is no study sponsor.

8.3.2 Investigator reporting:

For reportable deaths, the initial submission to the UNC IRB may be made by contacting the IRB Director or Associate Director. The AE/Unanticipated Problem Form is required as a follow up to the initial submission.

Other Reportable events:

For clinical drug trials, the following events are also reportable to the UNC IRB:

- Any adverse experience that, even without detailed analysis, represents a serious unexpected adverse event that is rare in the absence of drug exposure (such as agranulocytosis, hepatic necrosis, Stevens-Johnson syndrome).
- Any adverse event that would cause the sponsor to modify the investigators brochure, protocol or informed consent form, or would prompt other action by the IRB to assure protection of human subjects.
- Information that indicates a change to the risks or potential benefits of the research, in terms of severity or frequency. For example:
 - An interim analysis indicates that participants have a lower rate of response to treatment than initially expected.
 - Safety monitoring indicates that a particular side effect is more severe, or more frequent than initially expected.
 - A paper is published from another study that shows that an arm of your research study is of no therapeutic value.
- Change in FDA safety labeling or withdrawal from marketing of a drug, device, or biologic used in a research protocol.
- Breach of confidentiality
- Change to the protocol taken without prior IRB review to eliminate apparent immediate hazard to a research participant.
- Incarceration of a participant when the research was not previously approved under Subpart C and the investigator believes it is in the best interest of the subject to remain on the study.
- Complaint of a participant when the complaint indicates unexpected risks or the complaint cannot be resolved by the research team.
- Protocol violation (meaning an accidental or unintentional deviation from the IRB approved protocol) that in the opinion of the investigator placed one or more participants at increased risk, or affects the rights or welfare of subjects.

8.3.3 Investigator reporting:

Affiliate sites will inform study PI and primary site of any adverse events as described in sections 8.1, 8.2 and 8.3.

